5.5. Tertiary/Exploratory Endpoint Analysis

The exploratory analyses will be based on the FAS. These analyses will be descriptive in nature, and no adjustment for multiplicity will be performed. In addition, there will be no imputation for missing data or data collected on or after the receipt of additional standard-of-care therapy (for LN cohort) or treatment discontinuation unless otherwise specified below.

Summary statistics will be computed and displayed by treatment group and by visit, where applicable. Descriptive statistics for continuous variables will minimally include the number of participants, mean, SD, minimum, median, and maximum. For categorical variables, frequencies and percentages will be presented.

The analyses for participants in the LN cohort and participants in the IgAN cohort will be conducted and reported separately. Participants in each disease-specific cohort will be analyzed as randomized, regardless of actual treatment received.

5.5.1. Effect on Hematuria

The effect on hematuria will be summarized by category of RBCs in urine.

The RBCs in urine will be summarized at each time point by treatment group using frequency statistics for categorical variables.

In addition, the percentage of participants with < 10 RBCs will be summarized at each scheduled visit by calculating the point estimate and 2-sided 95% CI, based on exact confidence limits using the Clopper-Pearson method.

5.5.2. SF-36v2

For both cohorts, the SF-36v2 total score, Physical Component Summary (PCS), Mental Component Summary (MCS), and domain scores as defined in [Table 4](#) will be summarized by treatment group at baseline and each postbaseline time point using descriptive statistics for continuous variables for the observed value as well as the change from baseline.

The longitudinal changes in SF-36v2 scores will also be analyzed using the same MMRM method specified in Section [5.4.1](#). Data collected on or after receipt of additional standard-of-care therapy or treatment discontinuation will be assumed missing and handled in the MMRM as MAR.

Refer to Section [6.3.1](#) for a more detailed description of the SF-36v2 calculation and scoring methods.

Table 4: SF-36v2 Domain Scores

Scale	Number of Items	Definition of Scale
Physical Functioning (PF)	10	Limitations in physical activity because of health problems
Social Functioning (SF)	2	Limitations in social activities because of physical or emotional problems
Role Limitations Due To Physical Health (RP)	4	Limitations in usual role activities because of physical health problem
Bodily Pain (BP)	2	Presence of pain and limitations due to pain
General Health (GH)	5	Self-evaluation of personal health
Mental Health (MH)	5	Psychological distress and well-being
Role Limitations Due To Emotional Problems (RE)	3	Limitations in usual role activities because of emotional problems
Vitality (VT)	4	Energy and fatigue

Abbreviations: SF-36v2 = 36-item Short Form Health Survey Version 2

5.5.3. EQ-5D-5L

The EQ-5D-5L is a self-assessed, health-related QoL questionnaire. It is a measure of health status consisting of 2 parts. The first part assesses health in 5 dimensions including mobility, self-care, usual activities, pain/discomfort, and anxiety/depression. Each level is rated on a scale that describes the degree of problems in that area (ie, I have no problems walking about, slight problems walking, moderate problems walking, severe problems walking, or unable to walk). This part of the EQ-5D-5L questionnaire provides a descriptive profile that can be used to generate a health state profile. For example, a participant in health state 12345 would have no problems with mobility, slight problems with self-care (washing or dressing), moderate problems with doing usual activities, severe pain or discomfort and extreme anxiety or depression. The EQ-5D-5L health states can be represented by a single summary number (index value), which reflects how good or bad a health state is according to the preferences of the general population of a country/region. A health state index score will be calculated using a US-specific value set ([Pickard, 2019](#)). The second part consists of a visual analog scale (VAS) on which the participant rates their perceived health from 0 (the worst imaginable health) to 100 (the best imaginable health).

For both cohorts, the EQ-5D-5L index score and VAS score will be summarized by treatment group at baseline and each postbaseline time point using descriptive statistics for continuous variables for the observed value as well as the change from baseline.

The longitudinal changes in EQ-5D-5L scores will also be analyzed using the same MMRM method specified in Section [5.4.1](#). Data collected on or after receipt of additional standard-of-care therapy or treatment discontinuation will be assumed missing and handled in the MMRM as MAR.

Refer to Section [6.3.2](#) for a more detailed description of the EQ-5D-5L calculation and scoring methods.

5.5.4. Exploratory Biomarkers

Exploratory blood, urine, and kidney biomarker analyses will be documented in a separate biomarker SAP.

5.5.5. Time to CRR and PRR (LN Cohort Only)

For the LN cohort, time to CRR and time to PRR will be summarized using spot urine samples. Participants will be assigned as responders at the time of their CRR or PRR, respectively, or censored at the earliest of their treatment discontinuation time, receipt of additional standard-of-care therapy, study withdrawal or death, or at Week 50 if they have not responded or received additional standard-of-care therapy by then.

Kaplan-Meier cumulative distribution curves will be generated for each treatment group, and a log-rank test comparing the curves will be performed. A corresponding summary table will present the CDF estimate, the number of participants at risk, the number of participants responding, and the number of participants censored at each postbaseline time point by treatment group. The table will also present first quartile, median, and third quartile, along with corresponding 2-sided 95% CI, of time to response.

5.5.6. Overall Renal Response (LN Cohort Only)

For the LN cohort, overall renal response is defined as meeting either CRR or PRR.

Participants who receive additional standard-of-care therapy, who discontinue treatment prior to the endpoint assessment or who withdrawal from study will be considered nonresponders.

The percentage of participants meeting the criteria for overall renal response will be analyzed using a CMH test accounting for the stratification factor at Week 26 and Week 50 and will be summarized by treatment group by calculating the point estimate and 2-sided 95% CI based on exact confidence limits using the Clopper-Pearson method.

5.5.7. Time to UPCR > 50% Decrease (LN Cohort Only)

For the LN cohort, time to UPCR > 50% decrease from baseline will be summarized using spot urine samples. Participants will be assigned as responders at the time of their > 50% decrease from baseline in UPCR or censored at the earliest of their treatment discontinuation time, receipt of additional standard-of-care therapy, study withdrawal or death, or at Week 50 if they have not responded or received additional standard-of-care therapy by then.

Kaplan-Meier cumulative distribution curves will be generated for each treatment group, and a log-rank test comparing the curves will be performed. A corresponding summary table will present the CDF estimate, the number of participants at risk, the number of participants responding, and the number of participants censored at each postbaseline time point by treatment group. The table will also present first quartile, median, and third quartile, along with corresponding 2-sided 95% CI, of time to response.

5.5.8. FACIT-Fatigue (LN Cohort Only)

For the LN cohort, the FACIT-Fatigue score will be summarized by treatment group at baseline and each postbaseline time point using descriptive statistics for continuous variables for the observed value as well as the change from baseline.

The longitudinal changes in FACIT-Fatigue score will also be analyzed using the same MMRM method specified in Section 5.4.1. Data collected on or after receipt of additional standard-of-care therapy or treatment discontinuation will be assumed missing and handled in the MMRM as MAR.

Refer to Section 6.3.3 for a more detailed description of the FACIT-Fatigue calculation and scoring methods.

In addition, the proportion of participants who showed an improvement of at least 3 points for the FACIT-Fatigue scores will be summarized descriptively at each study visit by treatment group by calculating the point estimate and 2-sided 95% CI, based on exact confidence limits using the Clopper-Pearson method.

5.5.9. Anti-dsDNA and Anti-C1q antibodies (LN Cohort Only)

For the LN cohort, anti-dsDNA and anti-C1q antibodies will be summarized at baseline and each postbaseline time point by treatment group. Anti-C1q will be using descriptive statistics for the observed value as well as the change from baseline. Anti-dsDNA will be summarized in shift table by each postbaseline time point.

In addition, the proportion of participants with anti-C1q antibodies below the LLN will be summarized descriptively at each study visit by treatment group by calculating the point estimate and 2-sided 95% CI, based on exact confidence limits using the Clopper-Pearson method.

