	Absolute values and change from baseline in ravulizumab concentrations over time
To characterize the potential for immunogenicity of ravulizumab in adult participants with LN or IgAN	Incidence of ADAs over time
Safety (Both Cohorts)	
To characterize the safety and tolerability of ravulizumab in adult participants with LN or IgAN	Incidence of AEs and SAEs over time
Exploratory (Both Cohorts)	
To evaluate the efficacy of ravulizumab compared with placebo on hematuria in adult participants with LN or IgAN	Effect on hematuria as measured by 
Absolute value and change from baseline in RBC in urine from baseline to Week 26 and Week 50Percentage of participants with < 10 RBC/hpf
To assess quality of life based on participant-reported outcomes in adult participants with LN or IgAN based on treatment with ravulizumab compared with placebo	Change from baseline in SF-36 at Week 26 and Week 50
	Change from baseline in EQ-5D-5L at Week 26 and Week 50
To evaluate complement and autoimmune biomarkers in adult participants with LN or IgAN	Absolute values and change from baseline in levels of biomarkers in blood, urine, and kidney tissue at Week 26 and Week 50
Exploratory (LN Cohort Only)	
To assess the efficacy of ravulizumab in exploratory efficacy endpoints	Time to CRR and PRR (using spot UPCR)
	Percentage of participants with Overall Renal Response at Week 26 and Week 50 (CRR and PRR)
	Time to UPCR > 50% decrease from baseline (using spot UPCR)
To assess quality of life based on participant -reported outcomes	Change from baseline in FACIT-Fatigue score at Week 26 and Week 50

Objectives	Endpoints
To assess the efficacy of ravulizumab in other exploratory endpoints	Absolute values and change from baseline in anti-dsDNA and anti-C1q antibodies at Week 26 and Week 50
	Histology changes from baseline to Week 50
Exploratory (IgAN Cohort Only)	
To assess the efficacy of ravulizumab in exploratory efficacy endpoints	Slope of eGFR computed from baseline to Week 26 and Week 50

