24-h urine	
• Total protein, total creatinine, total albumin, total sodium, creatinine clearance, and protein to creatinine ratio, albumin to creatinine ratio.
Spot urine studies	
• Protein, albumin, creatinine, and protein to creatinine and albumin/creatinine ratio
Routine urinalysis and urine sediment	
• Albumin• Bilirubin• Blood• Erythrocytes• Glucose• Ketones• Leukocyte esterase

Table 13: Protocol-Required Laboratory Assessments

Laboratory Assessments	Parameters
	
 • Nitrite • pH • Protein • Specific gravity • Urobilinogen • Urine sediment: number of RBCs/high-power field and number of RBC casts^b
PK/PD and immunogenicity	
 • Serum PK • Serum PD (free and total C5) • Immunogenicity (ADA)
Other study-specific tests	
 • HCV PCR viral load, HBV antigen and serology panel • HIV-1 and HIV-2 antibody • Serum follicle-stimulating hormone (as needed in women of nonchildbearing potential only) • Serum or urine human chorionic gonadotropin pregnancy test (as needed for WOCBPs)^a • Complement: C3, C4, and CH50 • Autoantibody profile: ANA, anti-dsDNA, anti-Sm, anti-RNP, anti-Ro, anti-La, anti-C1q, anti-phospholipid antibodies (LN cohort only)
	
 • Anti-ds-DNA antibody: to be measured by ELISA at all visits as part of SLEDAI Assessment (LN cohort only)

^a Serum pregnancy test at Screening and End of Study Visit/Early Discontinuation Visit, and local urine pregnancy test at all other times as specified in Schedule of Assessments.

^b For participants in the IgAN cohort, eligibility for hematuria can be determined via the local laboratory.

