- Corticosteroid induction timing (prior to Screening, during Screening Period)
- Baseline SLEDAI-2K score: descriptive statistics (n, mean, median, SD, minimum, maximum)
- Baseline FACIT-Fatigue score: descriptive statistics (n, mean, median, SD, minimum, maximum)
- Baseline anti-dsDNA autoantibodies: titer ($\leq 1:160$, $\leq 1:640$, $\leq 1:2560$)
- Baseline anti-C1q autoantibodies: descriptive statistics (n, mean, median, SD, minimum, maximum) and frequency of participants with antibody levels $<$ LLN

For the IgAN cohort, the following additional disease characteristics will be summarized:

- Baseline 24-hour urine protein (g/day): descriptive statistics (n, mean, median, SD, minimum, maximum) and frequency of participants in the following categories: 1 to 2 g/day, > 2 g/day
- Baseline 24-hour UPCR (g/g): descriptive statistics (n, mean, median, SD, minimum, maximum)
- Time from eligibility biopsy to randomization (< 1 month, 1 to 3 months, 3 to 6 months, 6 to 12 months, 12 to 24 months, > 24 months)
- MEST-C score based on central pathology (M0, M1, E0, E1, S0, S1, T0, T1, T2, C0, C1, C2)

- C3 staining based on central pathology (0+, 1+, 2+, 3+)
- C4d staining based on central pathology (0+, 1+, 2+, 3+)
- C1q staining based on central pathology (0+, 1+, 2+, 3+)

The agreement between local and central pathology diagnosis will be assessed for each disease cohort by interobserver reliability analysis using the kappa statistic reported with 95% CIs. In addition, if central pathology results are limited then local pathology results may be summarized as well in the disease characteristic summary.

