6.6. Appendix 6: List of Abbreviations

Table 5 shows the abbreviations and acronyms that are used in this SAP.

Table 5: Abbreviations and Acronyms

Abbreviation or acronym	Explanation
ACE	Angiotensin-converting enzyme inhibitors
ADA	antidrug antibody
AE	adverse event
ANCOVA	analysis of covariance
anti-dsDNA	anti-double-stranded DNA
ARB	angiotensin II receptor blockers
ATC	Anatomical Therapeutic Chemical
BLQ	below the limit of quantification
CDF	cumulative distribution function
CI	confidence interval
C _{max}	maximum concentration
CMH	Cochran–Mantel–Haenszel
CRR	complete renal response
Ctrough	trough concentration
ECG	electrocardiogram
eCRF	electronic case report form
eGFR	estimated glomerular filtration rate
EQ-5D-5L	5-level EuroQol-5 Dimension
FACIT-Fatigue	Functional Assessment of Chronic Illness Therapy – Fatigue
FAS	Full Analysis Set
GMR	geometric mean ratio
IC	inclusion criteria
IgAN	immunoglobulin A nephropathy
IXRS	Interactive Voice/Web Response System
LLN	Lower limit of normal
LLOQ	lower limit of quantification
LN	lupus nephritis
MedDRA	Medical Dictionary for Regulatory Activities
MAR	missing-at-random
MSC	Mental Component Summary
mFAS	Modified Full Analysis Set
MMF	mycophenolate mofetil
MMRM	mixed effect model for repeated measures
MNAR	missing-not-at-random
NAb	neutralizing antibody
PD	pharmacodynamic(s)
PK	pharmacokinetic(s)
PPS	Per-protocol Set
PRR	partial renal response
PSC	Physical Component Summary
PT	preferred term (MedDRA)
QoL	quality of life
QTc	corrected QT
QTcF	QT interval corrected using Fridericia's formula
RAS	renin-angiotensin system

Table 5: Abbreviations and Acronyms

Abbreviation or acronym	Explanation
RBC	red blood cell
SAE	serious adverse event
SAS®	Statistical Analysis Software®
SAP	Statistical Analysis Plan
SD	standard deviation
SF-36v2	36-item Short Form Health Survey Version 2
SLE	systemic lupus erythematosus
SLEDAI-2K SELENA Modification	Systemic Lupus Erythematosus Disease Activity Index Safety of Estrogen in Lupus Erythematosus National Assessment Modification
SOC	system organ class (MedDRA)
TEAE	treatment-emergent adverse event
TESAE	treatment-emergent serious adverse event
UPCR	urine protein-to-creatinine ratio
VAS	visual analog scale
WHO-DRUG	World Health Organization Drug Dictionary

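### In the LN cohort, anti-C1q is counted against the lower instead of the upper limit of normal, and the anti-dsDNA categories overlap at baseline and are undefined on study

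*SAP*

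**What the plan says.** Protocol Section 3.1 sets the LN exploratory endpoint as "Absolute values and change from baseline in anti-dsDNA and anti-C1q antibodies at Week 26 and Week 50". The endpoint table in SAP Section 1.1 repeats it.

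SAP Section 5.5.9 then treats the two antibodies differently:

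- Anti-C1q, continuous: "Anti-C1q will be using descriptive statistics for the observed value as well as the change from baseline".
- Anti-C1q, categorical and in addition: "the proportion of participants with anti-C1q antibodies below the LLN will be summarized descriptively at each study visit by treatment group", with Clopper-Pearson 95% limits. The SAP abbreviation list expands LLN as "Lower limit of normal".
- Anti-dsDNA: "Anti-dsDNA will be summarized in shift table by each postbaseline time point". The section does not say what the shift categories are.

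The LN baseline list in SAP Section 6.2.1.2 repeats the anti-C1q limit: "Baseline anti-C1q autoantibodies: descriptive statistics (n, mean, median, SD, minimum, maximum) and frequency of participants with antibody levels" below the LLN. For anti-dsDNA it has the entry "Baseline anti-dsDNA autoantibodies: titer" with three bands: ≤ 1:160, ≤ 1:640 and ≤ 1:2560. Protocol Table 13 (Section 10.2) names ELISA as the anti-dsDNA assay but gives no reporting unit.

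SAP Appendix 5, which lists departures from the protocol-planned analyses, has one entry: hematuria becomes categorical because of the form in which the central laboratory reports it.

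**The concern.** Protocol Section 8.9.1 classes anti-C1q as an autoantibody, so the state of interest should be a raised level, and improvement should be a fall to normal. A count below the lower limit does not measure that. The rule would suit the complement component C1q, for which Protocol Section 2.2.1 links low levels to active LN. Because the limit appears both in the on-study analysis and in the baseline table, it is unlikely to be a single slip.

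For anti-dsDNA, the printed bands do not sort participants into separate groups. The on-study shift table has no categories to shift between. The move from a continuous to a categorical analysis is of the same kind as the hematuria change, which the sponsor did record.

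At stake is whether these tables can be read, and whether their categories are fixed before unblinded results are seen. No primary or secondary endpoint is involved.

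**Working it through.** The plan gives no figure for these proportions, so there is nothing to reproduce. The check compares the rules with each other and works out what they yield.

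**1. Direction of the anti-C1q limit.** Three places show how the documents treat related markers:

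- The SLEDAI-2K form (Protocol Section 10.12) scores DNA binding, the other autoantibody, as abnormal when it is above the laboratory's normal range.
- The same form scores complement as abnormal when CH50, C3 or C4 is below the lower limit.
- SAP Section 6.2.1.2 counts participants with low C3 and low C4, which matches the complement direction.

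The anti-C1q rule follows the complement direction. Under it, a participant who moves from above the upper limit to mid-range is classified exactly like one who stays raised: neither is below the LLN.

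**2. Size of the anti-C1q count.** Inputs: 40 ravulizumab and 20 placebo participants (SAP Section 3), all assumed to have a sample at the visit. The reference range is an assumption, because the documents give none.

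The exact 95% upper limit for 0/n is 1 − 0.025^(1/n). The lower limit for n/n is 0.025^(1/n). The table takes the case most favourable to the rule, in which every participant is normal.

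| Cut-off and assumption | n = 40 | n = 20 |
|---|---|---|
| Below LLN; LLN zero or absent | 0/40 (0 to 8.8%) | 0/20 (0 to 16.8%) |
| Below LLN; 2.5% of normals below it | 40 × 0.025 = 1.0 expected | 20 × 0.025 = 0.5 expected |
| Below LLN; 5% of normals below it | 40 × 0.05 = 2.0 expected | 20 × 0.05 = 1.0 expected |
| At or below ULN | 40/40 (91.2% to 100%) | 20/20 (83.2% to 100%) |

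Over the range shown, the printed rule gives a count at or near zero when every participant is normal. The upper-limit rule would count all of them.

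**3. Baseline anti-dsDNA bands, read as printed.**

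| Titre | Bands satisfied |
|---|---|
| 1:160 or lower | 3 |
| 1:320, 1:640 | 2 |
| 1:1280, 1:2560 | 1 |
| 1:5120 or higher | 0 |

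The three percentages could therefore total anything from 0% (all participants above 1:2560) to 300% (all at 1:160 or lower). If each participant is instead placed in the first band satisfied, the overlap disappears, but titres above 1:2560 still have no category.

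**4. The endpoint followed through the documents.** Protocol Section 3.1 and SAP Section 1.1 both require values and change for both antibodies. SAP Section 5.5.9 provides these for anti-C1q. For anti-dsDNA it provides only a shift table with unnamed categories. Appendix 5 is silent on this.

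**The case against.** Several stronger readings are tempting, and the documents do not support them.

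- *The planned anti-C1q result is lost.* It is not. The endpoint is value and change, and Section 5.5.9 provides both. The LLN proportion is an addition, and the SAP does not call it a response.
- *The proportion will be 0% in both arms.* That depends on the assay's range, which is not given. With a two-sided range a few participants would be counted.
- *The titre bands spoil the on-study analysis.* They appear only in the baseline list, and Section 5.5.9 does not refer to them. The on-study fault is that the shift categories are undefined.
- *An ELISA cannot be reported as a titre.* Table 13 names the method and not the unit. The laboratory may report titres or categories, which might explain the shift table.
- *Anti-dsDNA change is not analysed at all.* A shift table does describe change, by category.
- *No other lupus activity marker is analysed.* SLEDAI-2K (SAP Section 5.4.9) and C3 and C4 (Section 5.4.3) each have their own analysis.

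It is also fair to say that table specifications are in a separate Data Presentation Plan, which may print the bands more carefully, and that SAP Section 5.5 makes all of this descriptive.

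These arguments limit the point but do not remove it. None makes a count below the LLN register a return to normal, supplies a category above 1:2560 or adds the missing Appendix 5 entry.

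**Conclusion.** The point holds as a minor correction. The anti-C1q cut-off is on the wrong side of the range in both places where it is used, and the resulting proportion would be empty or uninformative. That rests on anti-C1q being abnormal when raised, which is inferred from its status as an autoantibody and from the SLEDAI-2K rule for anti-dsDNA. The numerical size rests on the assumed reference range: 0/40 and 0/20 if the LLN is zero or absent, or about 1 to 2 of 40 and 0.5 to 1 of 20 if 2.5% to 5% of normals lie below it. The baseline anti-dsDNA bands are faulty as printed whatever the assay. The change from a continuous to a categorical anti-dsDNA analysis is unrecorded, and its categories are undefined.

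The consequences are confined to exploratory, descriptive LN tables. The primary endpoint, alpha and sample size are unaffected.

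**What to change.** 1. In SAP Sections 5.5.9 and 6.2.1.2, replace the below-LLN count for anti-C1q with a count at or below the assay's upper limit of normal, or at or below its positivity cut-off if that is what the laboratory provides. State which limit is used.
2. Define anti-dsDNA categories that are mutually exclusive and complete, in the unit the laboratory reports, and use the same set for the baseline and shift tables. If titres are reported, one such set is ≤ 1:160; > 1:160 to 1:640; > 1:640 to 1:2560; > 1:2560.
3. If the laboratory reports quantitative anti-dsDNA values, also summarise observed value and change at Weeks 26 and 50, as the endpoint requires. If it does not, record the change to a categorical analysis in Appendix 5.

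The cost is SAP wording, the affected table shells and one query to the laboratory about range and unit. No new data are needed: the samples are already scheduled at Screening, Day 1, Week 26 and Week 50. Fixing the limits before unblinded LN results are seen avoids any question of a cut-off chosen afterwards.
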